Original, 1/22/2019	First full draft, January 22, 2019 (aka "V1") ; 2/4/19: Reviewed by FRC, Approved, minor edits. 2/7/19: PI responses to FRC. FRC OK'd move to PRMC. 2/22/19: Reviewed by PRMC, Approved. PRMC OK'd proceed to IRB with incorporations of edits from FRC and PRMC.
Original, Revision 1, 3/8/2019	Revision to original. Dosing schedule and imaging clarified; size of CPT to collect PBMCs clarified; Study Calendar completely rearranged & revised to improve clarity re: research-related tests (versus standard of care).
3/21/2019	PRMC approved revision dated 3/8/2019.
3/12/2019	IRB Submission – review of Version Date 3.8.2019
4/29/2019 5/03/2019	IRB Meeting Notification of IRB withheld approval – requested edits to Informed Consent form
5/7/2019	Changes made to informed consent form, resubmitted to IRB
5/13/2019	Medicare coverage analysis returned.
5/20/2019	IRB initial approval received.
Original, Revision 2, 6/27/2019	Minor clarifications to Study Calendar from the Medicare Coverage Analysis findings. Budget updated to include MCC member discount to SRF fees, and research-related costs.
7/3/2019	PRMC approved Revision 2, dated 27 June 2019.
10/15/2019	PRMC approved Protocol Version Date 9/ 27 /19
12/3/2019	OPEN TO ACCRUAL
Amendment 1, 11/18/2020	Protocol revised to relax eligibility criteria (cataracts, and 5 lesions for oligomets).
Amendment 2, 6/7/2021	Protocol revised to clarify follow-up timepoints post-treatment.
Amendment 3, 01/05/2022	Protocol revised to include PSMA scan.
Amendment 4, 06/14/2023	PI changed to [name]; [name] noted as external co-PI. [name] added as co-statistician; [name] removed from the personnel list
Amendment 5, Add date	Placeholder for future amendment.
Amendment 6, Add date	Placeholder for future amendment.

Figure 1. SCHEMA

Inclusion Criteria:	Exclusion Criteria:

 - Men ages 18 and older with recurrent prostate cancer following primary treatment of localized disease with either surgery or radiation - Recurrence defined as PSA ≥ 0.2 ng/dl following prostatectomy OR a PSA increase ≥ 2 above nadir following radiotherapy of primary tumor - ≤ 5 synchronous metastatic lesions on CT C/A/P and/or fluciclovine or prostate-specific membrane antigen scan - ECOG 0-2 	
 - Brain or CNS mets - Prior XRT/surgery to a metastatic site; orchectomy - Prior ADT for metastatic disease or as adjuvant therapy in past two years - Hx of fracture or spinal cord compression - Currently treated with abiraterone, enzalutamide, apalutamide, chemotherapy, immunotherapy or radioisotopes - Macular degeneration - Serum testosterone less than 50 ng/ml - Receipt of HCQ in the past 6 months

STUDY ENDPOINTS

Primary: 3-mos PAR-4 levels

Secondary:

Median Progression-Free Survival and 1-yr ADT-Free Survival up to 3 years
 HCQ Toxicity and Tolerability
 Quality of Life

Correlatives: PBMCs (days 0, 30, 60 of HCQ treatment), immune function and activation, systematic inflammation, and autophagy induction

TABLE OF CONTENTS	Pages
Title Page / Protocol History & Summary of Changes	1 / 3
SCHEMA	4
Table of Contents	5-6

1. STUDY OBJECTIVES

1.1 Primary Objective

Assess the rate of attainment of a 50% increase in tumor suppressor PAR-4 levels from baseline in patients treated with 90-days of hydroxychloroquine (HCQ) in combination with radiation or surgery for recurrent, oligometastatic prostate cancer.

We hypothesize the successful attainment of a 50% increase from baseline will occur among 50% or more of study participants within the three-months administration period of HCQ.

1.2 Secondary Objectives

- Median Progression-Free Survival (time to clinical progression)
- 1- and 3-year Androgen Deprivation Therapy (ADT) Free Survival
- HCQ Treatment toxicity (AEs and SAEs during HCQ administration) and radiation toxicity to be assessed and recorded utilizing the CTCAE v5.0. Surgical Complications will be scored using the Clavien-Dindo Classification (Appendix F).
- Immunological effect of HCQ by analyzing peripheral blood mononuclear cells (PBMCs) at day 0 and Day 30 of treatment, and also, Day 60 (+ 6 weeks) of treatment.
- Quality of life as measured by the EORTC QLQ-C30 + QLQ-PR25

2. BACKGROUND

2.1 Prostate Cancer and its Treatment

Among men in the U.S., prostate cancer is the most common cancer and the second most common cause of cancer mortality.¹ In 2018, an estimated 164,960 men will be diagnosed with this disease, representing 19% of all new cancer cases and 9% of male cancer-specific mortality.¹ The prevalence of prostate cancer is projected to rapidly rise over the next 15 years, stemming from “the greying of the U.S. population.” Given the link between increasing age and cancer, aging baby boomers will significantly increase cancer incidence and mortality. For the first time in two decades, there was an increase in rates of prostate cancer deaths from 2017 to 2018.²

Early stage prostate cancer has few symptoms while men with more advanced disease may experience significant dysfunction, including weak or interrupted urine flow, urinary urgency, frequency and pain and bloody urine.² Initial treatment options include surgery, external beam radiation or brachytherapy.²⁻⁴

2.2 Oligometastatic Prostate Cancer

Advanced prostate cancer commonly spreads to the bones, which can cause pain in the hips, spine, ribs or other areas.^{2,4-6} For advanced disease (metastases or recurrence), hormonal therapy in conjunction with surgery or radiation is used.⁷⁻⁹ Historically, treatment of these patients has comprised primarily androgen deprivation therapy (ADT), guided by the premise that aggressive treatment of the primary tumor and metastatic lesions conferred considerable morbidity and was unlikely to result in cure.^{4,7-8} The survival benefit of ADT is juxtaposed against significant sequelae including cardiovascular morbidity, skeletal fractures, diabetes, sexual dysfunction, and a decrease in cognitive function.¹⁰

Advancements in molecular testing have highlighted distinctly different mutations in the lesions of patients with limited metastatic prostate disease as compared to those of patients with diffuse metastatic disease, possibly explaining the different biologic behavior of these tumors.¹¹⁻¹³ Among men with limited metastatic disease, there is a potential benefit to treatment of oligometastatic prostate lesions.¹⁴ Previous studies have identified a potential delay in the initiation of ADT in men treated with stereotactic radiotherapy.^{15,16} Additionally, a prospective, multicenter trial showed that metastasis-directed therapy delayed initiation of ADT in patients with oligometastatic disease.¹⁷

Given increased rates of metastatic disease and projected increases in incidence and mortality, innovative enhancement of current prostate cancer treatment regimens is vital. Novel therapeutic approaches for oligometastatic prostate cancer are needed, given ADT-induced sequelae such as cardiovascular morbidity, diabetes, cognitive deficits and sexual dysfunction.

2.3 Prostate Apoptosis Response-4 (PAR-4): tumor suppressor protein

Prostate apoptosis response-4 (PAR-4) is a tumor suppressor protein that facilitates apoptosis in numerous types of cancer cells.¹⁸ PAR-4 is ubiquitously expressed in normal cells and tissues, but it is often inactivated, down-regulated or mutated in several types of cancer cells.^{18,19} PAR-4 sensitizes cells to the action of diverse therapeutic agents.¹⁸ The loss of PAR-4 in tumors contributes to recurrence and decreased overall patient survival. The baseline levels of PAR-4 secreted by normal cells are generally inadequate to cause massive apoptosis in cancer cells. Given the apoptosis-PAR-4 association, drugs that successfully bolster PAR-4 secretion constitute an important therapeutic advance.

2.4 Hydroxychloroquine (HCQ)

Chloroquine [CQ; (RS)-N'-(7-chloroquinolin-4-yl)-N, N-diethyl-pentane-1, 4-diamine] is an antimalarial drug introduced into clinical practice in 1947 for the prophylactic treatment of malaria and has been repurposed to treat inflammatory diseases such as rheumatoid arthritis and lupus. Hydroxychloroquine (HCQ) differs from chloroquine by the presence of a hydroxyl group at the N-ethyl substituent is beta-hydroxylated, but has similar pharmacokinetics to CQ, with quick gastrointestinal absorption and is eliminated by the kidney with minimal side effects on short term treatments.

Both CQ and HCQ are potent inhibitors of autophagy, a cellular survival process during starvation to maintain cellular energy by degradation of unnecessary or dysfunctional components through the actions of lysosomes. CQ and HCQ are lysosomotropic agents, which inhibit autophagy by raising the lysosomal pH, leading to inhibition of both fusion of autophagosome with lysosome and lysosomal protein degradation. Moreover, by inhibiting autophagy, CQ activates caspases and sensitizes the cells to apoptosis. These apoptosis-sensitizing features of HCQ or CQ enhance the anti-tumor effects of a broad range of cancer therapeutics.^{20,21} Institutional experiences with chloroquine administered concurrently with conventional therapy in adjuvant setting provided longer survival.²² These studies provide a basis for the hypothesis that hydroxychloroquine can elevate PAR-4 levels and thus provide tumor suppression systemically. Accordingly, HCQ and CQ are being studied either pre-operatively or in conjunction with chemotherapeutic agents or radiation.²³ Chloroquine has been found to induce PAR-4 expression and subsequently promote apoptosis of cancer cells and inhibit metastatic progression.^{23,24}

2.5 Study Rationale

Treatment of oligometastatic prostate cancer may be enhanced by the addition of hydroxychloroquine to either surgical resection or radiation treatment of metastatic lesions. Potential benefits of hydroxychloroquine include delayed disease progression and delayed initiation of ADT, lessening morbidity and increasing quality of life in men with oligometastatic prostate cancer. Our recent studies identified several small molecules that show robust secretion of PAR-4 in cell culture and mouse models, and secreted PAR-4 induces apoptosis of cancer cells.^{19,24} However, these small molecules are not FDA-approved for human use. We therefore sought to identify FDA-approved small molecule drugs that show robust secretion of PAR-4 in normal cells and can be repurposed for treatment of cancer. These studies (unpublished) identified HCQ as a potent inducer of PAR-4 secretion from normal cells under conditions that show no normal cell death.

As normal cells in any patient far outnumber cancer cells, FDA-approved PAR-4 secretagogues may play a valuable role in elevating systemic and local levels of PAR-4 protein, thereby inducing paracrine apoptosis in primary and metastatic prostate tumors. Systemic PAR-4 is also expected to induce apoptosis in circulating cancer cells that contribute to metastasis. PAR-4 produces apoptosis and HCQ is expected to produce elevated levels of PAR-4 secretion that will prevent the growth of tumors. HCQ has also been reported to both inhibit and enhance immune responses via changes in Th1, Th2, Th17 and Treg subsets and reduce inflammatory markers. It also acidifies lysosomes that potentially inhibits antigen presentation by antigen-presenting cells and can be measured with LysoSensor Yellow/Blue DND-160 by flow cytometry. HCQ blocks autophagy by preventing the fusion of the autophagosome with the lysosome, and auto- phagosome cargo protein p62/Sequestosome-1 (also known as the ubiquitin-binding protein), and microtubule-associated protein LC-3II levels (analyzed by Western blot analysis or IHC) are elevated in the normal cells, as well as tumor cells in the patient.

2.6 Study Hypothesis: In men who develop recurrent oligometastatic disease following primary treatment of prostate cancer, treatment with surgery or radiation in combination with administration of hydroxychloroquine (400 mg per day for a 90-day period) will induce an elevation of PAR-4 expression among a majority of participants within three months of HCQ administration.

We hypothesize successful attainment of a 50% increase in PAR-4 from baseline levels among 50% or more of participants within the 90-day administration period of HCQ.

3. PATIENT SELECTION – ELIGIBILITY

3.1 Inclusion Criteria

- 3.1.1 Males age 18 and over
- 3.1.2 Histologically confirmed prostate cancer that has recurred following primary definitive treatment of localized prostate cancer (either surgery, radiotherapy or both)
 - PSA biochemical recurrence defined as either:
 - PSA \geq 0.2 ng/dL following radical prostatectomy
 - PSA increase \geq 2 ng/mL above PSA nadir value following radiotherapy of primary tumor
- 3.1.3 Five or fewer synchronous metastatic lesions (on imaging) with no evidence of residual local disease
- 3.1.4 ECOG performance status 0 – 2 (see **Appendix A**)
- 3.1.5 Approval by screening eye exam (disqualifying baseline conditions listed in 3.2.2, below)
- 3.1.6 Ability to provide informed consent

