4.2 Enrollment Guidelines

Patients who have received previous treatment for prostate cancer with the intent to cure who have biochemical recurrence will undergo metastatic evaluation with imaging at baseline including fluciclovine or prostate-specific membrane antigen (PSMA) PET scan (preferred), bone scan, PET/CT and/or CT of the chest, abdomen, and pelvis as needed to assess for metastatic disease.

Biochemical recurrence for patients who have previously undergone radical prostatectomy is defined as a PSA ≥ 0.2 ng/dl. Patients who have biochemical recurrence following radical prostatectomy should have received postoperative radiotherapy to the prostate bed if no evidence of metastatic disease.

For patients who have previously undergone primary treatment of their prostate cancer with radiotherapy, biochemical recurrence is defined as an increase of 2 or more ng/dl above the nadir. Patients who have undergone primary radiotherapy will have pelvic MRI to rule out local disease as part of the requisite baseline imaging. Suspicious lesions within prostate bed will be assessed by biopsy.

Patients with 1-3 metastatic lesions on metastatic evaluation will be further screened per inclusion and exclusion criteria as noted above, Section 3. Initial localization of metastases will be recorded (node vs bone vs visceral).

Eligible patients will be identified by the principal investigator and co-investigators of this study. Potentially eligible patients will be screened in the University of Kentucky Markey Cancer Center clinics by the investigators, study personnel, and the Principal Investigator (PI). Upon obtaining proper consent, patients will be enrolled into the study.

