5.5 Duration of Therapy

In the absence of treatment delays due to adverse event(s), hydroxychloroquine treatment will continue for 3 months or until one of the following criteria applies:

- Disease Progression, assessed by standard of care and defined as either:
 - PSA progression (an increase in PSA > 25% above baseline at study entry), or
 - Symptomatic progression (increasing pain from metastatic lesion), or
 - Progression of baseline-detected lesions (soft-tissue lesions as assessed by RECIST and bone lesions as assessed by the MDA criteria (respectively, Appendix H.1 and Appendix H.2)).
Additionally, CT C/A/P and/or fluciclovine or PSMA PET scans may be performed at the time of either Symptomatic or PSA Progression at discretion of the treating physician.
 - Appearance of new metastatic lesions
- Intercurrent illness that prevents further administration of treatment
- Unacceptable adverse event(s)
- Patient decides to withdraw from the study
- General or specific changes in the patient's condition that render the patient unacceptable for further treatment in the judgment of the investigator

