
NOTES: * per standard of care ** at the discretion of the treating physician.
 
Legend: S = standard of care; R = research; PSA, prostate-specific antigen; PET, positron emission tomography scan; HCQ, hydroxychloroquine; PAR-4, prostate apoptosis response-4; PSMA, prostate-specific membrane antigen PET scan
 
1: Blood (1 tube) will be drawn at each of the 7 noted timepoints for PSA and PAR-4 levels; plasma is preferred (serum is acceptable). Timepoints may be +/- 72-hour window at Pre-study and Enrollment. For Day 14, Timepoints may be +/- 120-hour window. Timepoints may be +/- 28-day window at the 3-, 6- and 12-month f/u, coinciding with a clinic visit.
 
2: for collection of PBMCs (peripheral blood mononuclear cells): one tube per collection timepoint, slated for Day 0, Day 30 and Day 60. Day 0 and Day 30 timepoints have a +/- 14-day window. Day 60 has a +6 week window. This is explicated in greater detail in study lab manual.
 
3: QOL is assessed via EORTC QLQ-C30 + QLQ-PR25 at 4 timepoints 
 - at a clinic visit prior to initiation of HCQ - at a clinic visit; either the end of HCQ administration OR when HCQ is discontinued (if stop it early) - at 6-mos and 12-mos post-treatment. These final two QOL timepoints can be +/- 8 weeks, and conducted during a regularly scheduled, standard of care clinic visit. 
 
4: Requisite pre-study eye exam; Eye exam may be repeated during HCQ administration if vision complaints.
 
5: One tube of blood will be drawn at each of the 6 noted timepoints for serum PSA; this is standard of care for baseline and every 3 months (4 of the 6 draws), with two additional draws scheduled. Timepoints may be +/- 72-hour window at screening and enrollment.
 
6: Imaging at baseline, pre-study: Patients who have confirmed recurrent disease of the prostate are deemed ineligible for this trial. As such, all eligible patients will undergo standard of care imaging to identify metastases (initial evaluation of status/extent of recurrent disease), including: 6a: All eligible patients will undergo standard of care imaging to assess extent of metastatic disease at baseline; fluciclovine or PSMA PET scans are preferred; other scans (PET/CT scan, bone scan and/or CT of the chest, abdomen and pelvis) may be performed as needed at baseline to assess extent of metastatic disease, per standard of care. 6b: Additionally, eligible patients who have undergone radiation prior to study enrollment will have an MRI of pelvis (in addition to previously named imaging studies) to assess for recurrent local disease. Suspicious lesions of the prostate seen on MRI will be biopsied. 6c: Imaging on Study as work-up for disease progression: Once a patient is enrolled on-study, imaging to assess disease progression will proceed per standard of care, based on clinical indicators such as rising PSA and/or other clinical symptoms. Per RECIST 1.1, tumor re-evaluation scheduled every 6-8 weeks at the discretion of the treating physician based on clinical indicators. Notably, a rising PSA and/or other clinical symptoms could trigger a scan/imaging in an earlier timeframe.
 
7: Concomitant Medications will be assessed per standard of care at the discretion of the treating physician; during HCQ administration, Con Meds will be assessed with a particular focus on medications contraindicated for use with HCQ.
 
8: Height will be evaluated once while on-study. Height can either be assessed via the patient's medical record, and/or assessed directly (in conjunction with vital signs during a clinic visit)
 
9: ADT initiation: record date and reason for ADT initiation. Reasons for ADT initiation include: PSA/biochemical progression, Symptomatic Progression, Local Progression of baseline-detected lesions (either soft-tissue or bone lesions), or Appearance of new metastatic lesions.
											

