11.3 Four Types of Disease Progression

1. **PSA or Biochemical Progression:** defined as a PSA increase of $\geq 25\%$ and ≥ 2 ng/mL if PSA was ≥ 2 ng/mL from baseline (OR a PSA increase of $\geq 25\%$ if PSA was < 2 ng/mL at study enrollment).
2. **Symptomatic Progression:** defined as increasing pain from baseline-detected metastatic lesion. Time to first symptomatic event will be calculated from study enrollment until the event of symptoms due to metastatic disease.
3. **Local Progression of baseline-detected lesions depend on site:**
 - 3a. ***soft-tissue metastatic lesion:*** local progression is defined as an increase of $\geq 20\%$ in the largest tumor dimension with a minimum absolute increase of 5 mm. All lesions are considered target lesions, irrespective of size, if they are suspicious on choline PET-CT. See Appendix H.1 for RECIST v1.1.
 - 3b. ***bone metastases:*** local progression is assessed using the MD Anderson Cancer Center-criteria²⁶⁻²⁷, and defined as a $\geq 25\%$ increase in size of a measurable lesion or a $\geq 25\%$ increase in the size of ill-defined lesions on CT considered to be progression. MDA bone-specific response criteria in Appendix H.2.
4. **Distant Progression:** appearance of new metastatic lesions

11.4 Definition of Disease Assessments to evaluate Progression-Free Survival and ADT-Free Survival

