11.4.2 Progression-Free Survival (time to clinical progression)

Four types of progression are defined in 11.3. Progression is calculated from time of study enrollment until progression (per the 4 specified definitions) or death. Events for PFS are:

1. PSA or biochemical progression: defined as a PSA increase of $\geq 25\%$ and ≥ 2 ng/mL (if PSA was ≥ 2 ng/mL from baseline)
2. Symptomatic progression: increasing pain from metastatic lesion
3. Local progression of baseline-detected lesions: each metastasis is a target lesion independently assessed as:
 - soft-tissue lesions assessed per RECIST v1.1 (Appendix H.1)
 - bone lesions assessed per MDA bone-specific response criteria (Appendix H.2)
4. Distant progression: appearance of new metastatic lesions.

If an event is identified, then the time to the event will be recorded as the first instance where any of the above four situations occur.

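### Entry requires no local disease, but no PFS event type covers later recurrence in the prostate or prostate bed, so such a relapse counts only if and when the PSA limb, another event or death also occurs

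*Combined protocol and SAP*

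**What the plan says.** **Entry.** Inclusion criterion 3.1.3 requires "Five or fewer synchronous metastatic lesions (on imaging) with no evidence of residual local disease". Section 4.2 adds, for the baseline work-up, that "Suspicious lesions within prostate bed will be assessed by biopsy". Note 6 to the Study Calendar (section 10) states that "Patients who have confirmed recurrent disease of the prostate are deemed ineligible for this trial". The plan thus treats disease at the primary site as separate from metastatic disease.

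**PFS.** Section 11.4.2 says: "Progression is calculated from time of study enrollment until progression (per the 4 specified definitions) or death". It then lists the events:

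1. "PSA or biochemical progression: defined as a PSA increase of" at least 25% and at least 2 ng/mL, for a baseline PSA of 2 ng/mL or more. Section 11.3 adds that a 25% rise is enough when PSA at enrollment is below 2 ng/mL.
2. Increasing pain, tied to a metastatic lesion.
3. Local progression, which here means growth of the metastases seen at baseline.
4. "Distant progression: appearance of new metastatic lesions".

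The event date is the first occurrence of any of these four. Section 11.3 defines its fourth type in the same terms ("appearance of new metastatic lesions"), and the list in 5.5 has the same item ("Appearance of new metastatic lesions").

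**The concern.** Return of disease in the prostate or prostate bed is relapse of the cancer under study, and its absence was a condition of entry. The rationale in section 2.5 also expects PAR-4 to act on primary as well as metastatic tumors. If such a relapse is not an event, a man with a proven recurrence stays at risk in the Kaplan-Meier estimate until something else happens to him. Compared with a definition that counts local recurrence, the error runs one way: PFS can be too long but never too short. At stake are the median and the time-point PFS rates promised in 13.3.2.

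**Working it through.** The plan states no figure on this point, so the check has three parts.

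**1. Does any event type cover a new lesion in the prostate or bed?**

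- *PSA:* not tied to a site, so it counts if the threshold is reached.
- *Symptoms:* no; the pain must come from a metastatic lesion.
- *Local progression:* no; it concerns lesions present at baseline, each of them a metastasis, and 3.1.3 rules out local disease at baseline.
- *Distant progression:* no; it concerns new metastatic lesions.
- *Appendix H.1:* it lists new malignant FDG uptake as progressive disease, but its title limits it to soft-tissue metastatic lesions, and it enters PFS only through the local-progression item.

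Only the PSA limb can pick up a recurrence confined to the primary site.

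**2. How much PSA rise does that limb need?** Let B be baseline PSA in ng/mL. Under 11.3 the limit is 1.25 × B if B < 2, and the larger of 1.25 × B and B + 2 if B ≥ 2. The two terms are equal when 0.25 × B = 2, that is B = 8, so from 2 to 8 the 2 ng/mL minimum sets the limit. The baselines below are illustrative; the documents give no entry PSA distribution.

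| B | 1.25 × B | B + 2 | Limit | Rise needed |
|---|---|---|---|---|
| 1 | 1.25 | not used | 1.25 | 25% |
| 2 | 2.5 | 4 | 4 | 100% |
| 4 | 5 | 6 | 6 | 50% |
| 8 | 10 | 10 | 10 | 25% |
| 10 | 12.5 | 12 | 12.5 | 25% |

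Example (assumed values): entry PSA 4.0, local recurrence imaged at 5.5. The rise is 1.5 ng/mL, or 1.5/4.0 = 37.5%. The limit is 6, so none of the four types is met.

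The reference is baseline, not nadir, and site-directed treatment starts two weeks after HCQ does (5.3). If PSA first falls, the gap widens. Example (assumed values): entry 10, fall to 1, recurrence proven at 4; the limit is still 12.5.

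Detection below the limit is foreseeable. Note 6c bases on-study imaging on rising PSA or symptoms, with no numeric threshold. The PSA row of the calendar has six entries (screening, enrollment, day 30, day 90, 6 months, 1 year), which matches the six draws in note 5. That leaves none at years 2 and 3, although follow-up runs to three years (5.6).

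**3. What is one missed man worth?** Assume all 20 planned men are analyzed, with no censoring before the landmark. One man is 1/20 = 5 percentage points. With 10 counted events the reported rate is 1 − 10/20 = 50%. If one, two or three further men had a local recurrence and no other event by then, the rate counting those recurrences would be 45%, 40% or 35%.

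**The case against.** The strongest reply is that the PSA limb has no anatomical site and already catches local recurrence, usually before imaging does, because imaging is itself prompted by PSA or symptoms. A man drops out of the count altogether only if his recurrence is found below the limit, his PSA never reaches it later, and no other event follows. Pelvic MRI is a baseline procedure only. Baseline screening, and the bed radiotherapy that 4.2 expects after prostatectomy, should make the case uncommon. PFS is a descriptive, single-arm secondary endpoint with no test or decision attached.

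Much of this stands, and it limits the point. A reader might infer that every confirmed local recurrence is counted as progression-free. The documents do not support that: recurrences that reach the PSA limit are events, though possibly late.

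A reader might also infer that ADT-free survival is affected, because note 9 has no local-recurrence reason for starting ADT. It is not. Note 9 introduces its reasons as examples, and 11.4.1 counts any ADT start or death, whatever the reason.

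The reply does not remove the gap. The endpoint definition is a closed list, and whether a proven relapse counts should not depend on where PSA stands on the day it is found.

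**Conclusion.** The gap holds in this limited form. Confirmed recurrence in the prostate or prostate bed is not a PFS event in its own right. One found below the PSA limit is dated late, or is missed if nothing else follows. The effect can only overstate PFS.

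Each man missed at a landmark is worth 5 points, assuming 20 men analyzed and no censoring. A reader might multiply this by a guessed recurrence rate to get a total bias. The documents give neither the rate of local recurrence, nor the share found below the PSA limit, nor the entry PSA values, so no total can be defended. The primary PAR-4 analysis and the sample size are unaffected. The definition should be corrected, but the point does not threaten the trial's main conclusion.

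**What to change.** In 11.3 and 11.4.2 add a separate fifth event type: *confirmed recurrence in the prostate or prostate bed (biopsy-proven, or unequivocal on imaging where no biopsy is done), dated at first detection*. Change 'four' to 'five' wherever the types are counted.

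Do not place it under distant progression. That would mislabel it and, because 11.4.1 links distant progression to indications for ADT, could create a clinical rule by cross-reference.

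Optionally add a matching reason code in note 9, for record-keeping only. Sections 5.5 and 11.4.1 must be reconciled with the amended list; no view is taken here on when HCQ stops or ADT starts.

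The cost is definition wording and, if wanted, one case report form code, with no new test or visit. The downsides are a slightly shorter PFS and an event found only through clinically triggered imaging, so its timing will be irregular; the report should say so.
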